TP-013, Rev 03 PROTOCOL SYNOPSIS FOR CLINICALTRIALS.GOV**HHC-IRB NUMBER: HHC-2020-0086****IRB APPROVAL DATE: 10/13/2020**

TITLE	Dislodgment Infiltration Phlebitis Prevention Eliminating Restarts (DIPPER)
SPONSOR	Lineus Medical
FUNDING ORGANIZATION	Lineus Medical
STUDY START DATE	June 2020
RATIONALE	Accidental IV catheter dislodgement and other mechanical complications (e.g., infiltration, phlebitis, infection, and occlusion) in hospitalized patients are very common. IV catheter mechanical complications increase costs and put patients at increased risk. SafeBreak Vascular is designed to separate into two pieces when a certain threshold of force is applied to an IV administration line. The purpose of this medical device investigation is to determine SafeBreak Vascular's impact on clinical care (e.g., delay of therapy) and its' impact on other IV catheter mechanical complications when compared to a control group of patients not using the device.
STUDY DESIGN	Prospective randomized clinical trial
PRIMARY OBJECTIVE	The primary objective of this study is to determine if the use of SafeBreak Vascular results in a delay in therapy that is non-inferior to the delay in therapy for the control group, and if so, if SafeBreak Vascular is superior.
SECONDARY OBJECTIVES	The secondary objective is to estimate the reduction of other peripheral IV (PIV) catheter mechanical complications including dislodgement, infection, phlebitis, infiltration, occlusion, as well as blood/fluid spillage and PIV restarts when compared to the control group.
NUMBER OF SUBJECTS	Up to 146 total (73 in each arm). This sample size allows for 10% of the subjects to abandon therapy before the normal completion of treatment.
SUBJECT SELECTION CRITERIA	Inclusion Criteria: 
• All patients admitted into the hospital to one of the following units: Neuro, Neuro/Step Down Epilepsy Pulmonary, Cardiothoraci, Surgery/Step Down; Medicine/Step Down, Vascular Thoracic

	
Surgery/Step Down, B8- Surgery, B7E – Medicine/Step Down, B5-Vascular Thoracic Surgery
 
 • Patients of any gender may participate • Participants able to provide informed consent or have a legally authorized representative or Next of Kin immediately available to provide informed consent • Patients must have peripheral IV catheter access or need and are planned to have peripheral IV catheter access placed that is anticipated to last a minimum of 24 hours. • Patients must be receiving intermittent or continuous infusion, or have immediate plans to begin an intermittent or continuous infusion • The patients must be at least 18 years of age with no upper age limit. 
Exclusion Criteria:
 
 • Unable to obtain informed consent or without an available LAR or Next of Kin to provide surrogate informed consent • Age less than or equal to 17 • Patient on comfort care only • Predicted to have an IV infusion that lasts less than 24 hours. • Patient admitted from ED refuses to have new PIV catheter placed by IV team. • Patient has two or more peripheral IV catheters at the same time • Patient enrolled in a subject drug or device study at the time of enrollment • Investigator discretion that patient is not suitable for the study • Patient is COVID-19 positive • Patient is receiving an IV infusion with gravity tubing
SUBJECT DEVICE / INTENDED USE	SafeBreak is intended to stop fluid flow and prevent blood loss or fluid spillage in the event of excessive tension (4 ±1 lbs of force) occurs across a peripheral IV

	administration line in adults and adolescent populations eighteen (18) years of age or older. SafeBreak Vascular may be used only with electronic pumps for intermittent infusion or continuous infusion.
CONTROL GROUP	Participants with current standard of care for peripheral IVs.
DURATION OF SUBJECT PARTICIPATION AND DURATION OF STUDY	Study Participation Duration: Subjects in both groups will be followed for up to 7 days, or until the patient is discharged, or until IV access is discontinued. Duration of the Study: The study is expected to last at least two and up to three months.
EFFICACY EVALUATIONS	The primary and secondary objectives address the efficacy of the SafeBreak device.
PRIMARY ENDPOINTS	The primary endpoint is the time to re-start therapy following a mechanical complication with the catheter.
SECONDARY ENDPOINTS	Comparison of occurrence of mechanical complications (e.g., dislodgement, infection, infiltration, phlebitis, occlusion) as well as blood loss, fluid spillage and PIV restarts
SAFETY EVALUATIONS	The research team will evaluate all enrolled subjects at least twice daily for all adverse events and safety concerns and will document and communicate any concerns to the Investigator.

TP-013, Rev 03 STAT PLAN SYNOPSIS FOR CLINICALTRIALS.GOV**HHC-IRB NUMBER: HHC-2020-0086****IRB APPROVAL DATE: 10/13/2020**

TITLE	Dislodgment Infiltration Phlebitis Prevention Eliminating Restarts (DIPPER)
SPONSOR	Lineus Medical
FUNDING ORGANIZATION	Lineus Medical
STUDY START DATE	June 2020
RATIONALE	Accidental IV catheter dislodgement and other mechanical complications (e.g., infiltration, phlebitis, infection, and occlusion) in hospitalized patients are very common. IV catheter mechanical complications increase costs and put patients at increased risk. SafeBreak Vascular is designed to separate into two pieces when a certain threshold of force is applied to an IV administration line. The purpose of this medical device investigation is to determine SafeBreak Vascular's impact on clinical care (e.g., delay of therapy) and its' impact on other IV catheter mechanical complications when compared to a control group of patients not using the device.
STUDY DESIGN	Prospective randomized clinical trial
PRIMARY OBJECTIVE	The primary objective of this study is to determine if the use of SafeBreak Vascular results in a delay in therapy that is non-inferior to the delay in therapy for the control group, and if so, if SafeBreak Vascular is superior.
SECONDARY OBJECTIVES	The secondary objective is to estimate the reduction of other peripheral IV (PIV) catheter mechanical complications including dislodgement, infection, phlebitis, infiltration, occlusion, as well as blood/fluid spillage and PIV restarts when compared to the control group.
NUMBER OF SUBJECTS	Up to 146 total (73 in each arm). This sample size allows for 10% of the subjects to abandon therapy before the normal completion of treatment.

SUBJECT DEVICE / INTENDED USE	SafeBreak is intended to stop fluid flow and prevent blood loss or fluid spillage in the event of excessive tension (4 ± 1 lbs of force) occurs across a peripheral IV administration line in adults and adolescent populations eighteen (18) years of age or older. SafeBreak Vascular may be used only with electronic pumps for intermittent infusion or continuous infusion.
CONTROL GROUP	Participants with current standard of care for peripheral IVs.
EFFICACY EVALUATIONS	The primary and secondary objectives address the efficacy of the SafeBreak device.
PRIMARY ENDPOINTS	The primary endpoint is the time to re-start therapy following a mechanical complication with the catheter.
SECONDARY ENDPOINTS	Comparison of occurrence of mechanical complications (e.g., dislodgement, infection, infiltration, phlebitis, occlusion) as well as blood loss, fluid spillage and PIV restarts
SAFETY EVALUATIONS	The research team will evaluate all enrolled subjects at least twice daily for all adverse events and safety concerns and will document and communicate any concerns to the Investigator.
STATISTICAL ANALYSIS	
Primary Objective Test:
 
To demonstrate that the average time per 24 hours that therapy is delayed due to PIV mechanical complications is non-inferior with SafeBreak Vascular to that of the standard of care.
 
The secondary objective does not include a hypothesis test; estimation techniques will be used.

	
To test the Primary Objective:
 
 a. Of non-inferiority, the 24-hour delay of therapy due to PIV mechanical complications, SafeBreak Separations, and SafeBreak device failures of the SafeBreak group and PIV mechanical complications in the Control group will be compared with a non-inferiority Wilcoxon Rank-Sum test; b. Of inequality, the mean delay of therapy due to PIV mechanical complications, SafeBreak Separations, and SafeBreak device failures of the SafeBreak group and PIV mechanical complications in the Control group will be compared with a standard (inequality) Wilcoxon Rank-Sum test. 
To analyze Secondary Objective:
 
 a. The proportion of patients who experience PIV mechanical complications during the course of therapy will be estimated using a Kaplan-Meier time-to-event analysis. The proportions and counts of total mechanical complications will be compared between groups using a Chi-square analysis, Fisher's Exact Test, or Poisson regression as appropriate. b. Secondary endpoints include rates of IV restarts, blood/fluid spillage, dislodgement, infiltration, phlebitis, occlusion, and infection. The analysis population will be the Per Protocol population; the analysis method permits censoring at the time the patient exits or completes the study if this is prior to 7 days. 
Missing data that is not endpoint data will be ignored in reporting.

RATIONALE FOR NUMBER OF SUBJECTS	
Sample size rationale:
 
A total of 66 patients per group will provide 80% power at $\alpha=0.05$ to demonstrate non-inferiority of SafeBreak. An additional 10% will be enrolled to accommodate drop-out prior to therapy completion, for a total of 146 subjects.

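### Primary test: line interruptions that stop therapy count for SafeBreak but, read literally, not for Control, and the endpoint wording does not match items a and b

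*SAP*

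**What the plan says.** The PRIMARY OBJECTIVE, the same in Protocol and SAP, asks whether SafeBreak "results in a delay in therapy that is non-inferior to the delay in therapy for the control group", and then whether it is superior. It sets no limit on the cause of the delay.

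The PRIMARY ENDPOINTS entry is narrower: "The primary endpoint is the time to re-start therapy following a mechanical complication with the catheter". In the SAP's STATISTICAL ANALYSIS section, the Primary Objective Test is likewise limited in cause. It takes a daily average and asks whether the time "that therapy is delayed due to PIV mechanical complications is non-inferior with SafeBreak Vascular to that of the standard of care". Neither mentions separations or device failures.

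Items a and b, which specify the tests, use a third definition that differs by arm. Both set against each other the delay from "PIV mechanical complications, SafeBreak Separations, and SafeBreak device failures of the SafeBreak group and PIV mechanical complications in the Control group". Separations and device failures thus enter the SafeBreak total, and nothing beyond catheter-type complications enters the Control total.

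Mechanical complications are described by an open list in SECONDARY ENDPOINTS: "mechanical complications (e.g., dislodgement, infection, infiltration, phlebitis, occlusion". Spillage and restarts are added outside that list ("as well as blood loss, fluid spillage and PIV restarts"). Neither document says whether an accidental tubing disconnection, or a failure of the standard administration set, counts as delay.

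**The concern.** The device acts on the administration line, not on the catheter. If a pull separates SafeBreak and leaves the catheter in place, the resulting delay is counted. If a similar pull takes a control line apart and leaves the catheter in place, therapy also stops, but under the wording of items a and b the delay has no clear place in the Control total. The same holds for a line component that fails: it is counted if it is SafeBreak and not named if it belongs to the standard set.

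Two things are at stake. First, the measured difference would not be the difference in delay that the objective names, since some Control delay would be left out. Second, three statements of one primary variable disagree on whether separations and device failures belong in it, so the result could depend on which statement the analyst follows.

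**Working it through.** **1. The definitions side by side**

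| Where | SafeBreak delay | Control delay |
|---|---|---|
| Primary objective | any cause | any cause |
| Primary endpoint | catheter mechanical complication | catheter mechanical complication |
| Primary Objective Test | PIV mechanical complication | PIV mechanical complication |
| Items a and b | PIV mechanical complication, separation, device failure | PIV mechanical complication |

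Only the last row differs by arm, and it is the one that would be programmed.

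**2. The plan's own figure.** 66 × 1.10 = 72.6, rounded up to 73 per arm, and 2 × 73 = 146, as stated. The 66 cannot be reproduced, because no margin, standard deviation (SD) or sidedness is given. Neither figure turns on this point.

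**3. Direction.** Let x be the mean Control delay from line-only events that goes uncounted. The observed difference (SafeBreak minus Control) is then the true difference plus x, with x ≥ 0. That makes both steps harder to pass.

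**4. Why separations and failures must stay in.** Normal approximation with 66 per arm, rank-sum efficiency 3/π = 0.955 and one-sided 0.025 (assumed):
- SE = √(2 / (66 × 0.955)) = 0.178 SD.
- The margin that gives 80% power is (1.960 + 0.842) × 0.178 = 0.499 SD.
- If device-caused delay of x SD were dropped from SafeBreak, type I error at the margin would be Φ(x/SE − 1.960). This is 4.7%, 8.1% and 20% for x = 0.05, 0.1 and 0.2, against 2.5%.

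**5. Shift in the estimate.** All rates from here on are assumptions: line pulls in 10% to 30% of patients, 20 minutes' mean delay per pull, one quarter to three quarters of control pulls line-only, and follow-up uniform on 1 to 7 days. The mean of 1/days is ln 7 / 6 = 0.324. The uncounted Control delay is then:
- low: 0.10 × 0.25 × 20 × 0.324 = 0.16 min per 24 h
- middle: 0.20 × 0.50 × 20 × 0.324 = 0.65 min per 24 h
- high: 0.30 × 0.75 × 20 × 0.324 = 1.46 min per 24 h

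**6. Rank-sum test without a margin, equal true delay.** Simulated with 66 per arm, and with 20% of patients in each arm also having another complication of mean 60 minutes. A one-sided 5% test calls SafeBreak worse in about 8% (low), 20% to 23% over repeated runs (middle) and 62% (high) of trials. With no line-only events it is 5%. This shows how far the ranks shift. It is not item a, which has a margin.

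**7. Non-inferiority with a margin** (same set-up, one-sided 2.5%, margin assumed).
- Middle case at 0.5 min per 24 h: passes in 98.5% of trials, against 98.3% with no line-only events. At 1 min: 99.4% against 99.3%. These differences are simulation noise.
- High case: 97.5% at 2 min and 100% at 5 min.

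The reason is the mass of zeros. In the middle case 0.8 × 0.8 = 64% of SafeBreak patients have no delay, and subtracting any positive margin ranks them below every control patient. If delay were instead continuous and the margin only just gave 80% power, step 4's approximation would give power Φ((0.499 − x)/0.178 − 1.960), which is 61% at x = 0.1 SD and 39% at x = 0.2 SD. So the effect on non-inferiority depends on the margin and on the spread of delay, and the documents give neither.

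**8. Superiority when the device truly helps.** With a large assumed benefit (other complications 10% against 40%, 5 minutes per separation against 60 per dislodgement, pulls in 20%), superiority is found in 91% of trials when one quarter of control pulls are line-only and 82% when half are. Under another assumed benefit, power falls from about 69% to about 43% when half are line-only. Both are orders of magnitude only.

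**The case against.** The strongest reply is that the asymmetry is mostly correct accounting. SafeBreak separations and failures cannot happen in Control. They are delay caused by the intervention, and step 4 shows that leaving them out would flatter the device. A reader might infer that listing them for one arm is itself unfair; the documents do not support that. The usual control result of a hard pull, dislodgement, is already counted, and ordinary tubing disconnections are not named for SafeBreak either. All of this stands. It narrows the gap to line-only interruptions in Control.

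Next, the complication list is open, and both documents are synopses, so a full protocol or case report form may count control disconnections. This stands in part. The zero-delay reading is the literal one, since the endpoint is tied to the catheter, but it is not an explicit exclusion. Nor does the separate listing of spillage prove that the sponsor had line disconnections in mind, since spillage can also follow dislodgement. If the open list is meant to cover them, the plan should say so and not leave it to judgement at the bedside.

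Finally, any bias is conservative and every rate is assumed. Both are true. They limit the weight of the point but do not remove it, because superiority is a stated part of the primary objective and the estimated difference should match the delay that the objective names.

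**Conclusion.** The point holds in limited form. Items a and b rightly include separations and device failures, but as worded they give no place to control line interruptions without a catheter complication. The endpoint and the Primary Objective Test disagree with items a and b. That disagreement is plain from the text and needs no assumption.

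The bias runs against the device and cannot produce a false non-inferiority or superiority claim. Its size cannot be derived from the documents. Under the assumed rates it moves the estimated difference by 0.16 to 1.46 min per 24 hours and reduces power for superiority. It has little effect on non-inferiority unless line-only events are common and the margin is very small.

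Two stronger inferences should be resisted. One is that superiority becomes almost unreachable: the low rate of superiority findings under equal delay is a lower false-positive rate, not lost power, and with a true benefit superiority is still found (step 8). The other is that equal delays would commonly fail non-inferiority: the 20% to 23% figure comes from a test without a margin.

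**What to change.** Keep separations and device failures. Define the primary variable once, for both arms, as total delay per 24 hours from any unplanned interruption of the peripheral IV infusion: a catheter complication, a separation or disconnection of the line (SafeBreak or ordinary tubing), or failure of a line component (SafeBreak or standard set). Use that definition in the primary endpoint, the Primary Objective Test and items a and b. Record these events on the same form in both arms, and report the current definition as a sensitivity analysis.

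The cost is SAP and endpoint wording plus one added event category for control patients, who are already evaluated at least twice daily under SAFETY EVALUATIONS. The category has to be in place while data are collected, because disconnections that were not recorded cannot be recovered at analysis.

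### Kaplan-Meier with normal completers censored overstates the stated proportion of patients with a complication during therapy; cumulative incidence estimates it directly

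*SAP*

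**What the plan says.** The SAP, Statistical Analysis, part (a) of the secondary objective: "The proportion of patients who experience PIV mechanical complications during the course of therapy will be estimated using a Kaplan-Meier time-to-event analysis". The next sentence compares proportions and counts of complications between groups by Chi-square, Fisher's exact test or Poisson regression.

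Part (b) adds "The analysis population will be the Per Protocol population" and says that the method "permits censoring at the time the patient exits or completes the study if this is prior to 7 days". No other censoring rule appears, and no day is named at which the curve is read.

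The Protocol, Duration of Subject Participation, defines when follow-up stops: "Subjects in both groups will be followed for up to 7 days, or until the patient is discharged, or until IV access is discontinued".

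Elsewhere the SAP separates early abandonment from normal completion. Number of Subjects: "This sample size allows for 10% of the subjects to abandon therapy before the normal completion of treatment". Rationale for Number of Subjects: "An additional 10% will be enrolled to accommodate drop-out prior to therapy completion".

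The paragraph on the primary objective test also states that the secondary objective carries no hypothesis test and relies on estimation.

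**The concern.** The stated target is what happens to patients while they are on therapy. Kaplan-Meier treats a censored patient as still able to have the event later, unobserved. That suits a patient who drops out with the infusion still needed. It does not suit a patient whose IV was removed as planned, because that patient's chance of a complication during therapy is then zero.

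With such patients censored, one minus Kaplan-Meier answers a different question: the risk by a given day had the IV stayed in place. Even that reading requires end of therapy to be independent of complication risk, which the SAP does not state.

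The secondary objective is to estimate how far complications are reduced. If the Kaplan-Meier percentages are reported under the SAP's wording, they overstate what patients experience. The report could also carry two different proportions for one endpoint: the Kaplan-Meier figure and the crude proportion behind a Chi-square or Fisher comparison.

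**Working it through.** **The plan's own figure.** No figure is stated for this analysis. The only nearby number is enrolment: 66 × 1.10 = 72.6, rounded up to 73 per arm, 146 in total. It reproduces, and nothing below depends on it.

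**Direction, without assumed rates.** At each complication time let d be the number of complications and Y the number at risk.
- One minus Kaplan-Meier adds up S_KM(t−) × d/Y, where S_KM falls only at complications.
- Cumulative incidence adds up S_all(t−) × d/Y, where S_all falls at complications and at normal completions.

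S_all is never above S_KM, so one minus Kaplan-Meier is never below cumulative incidence. It is strictly larger once a completion precedes a later complication.

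**Size, on assumed rates.** The SAP Rationale says only that complications "in hospitalized patients are very common". All inputs here are therefore assumptions:
- complication rate h, constant, 0.05 to 0.50 per day (central 0.10);
- normal therapy-end rate g, constant and independent of h, 0.15 to 0.50 per day (central 0.25);
- no therapy end in the first 24 hours. The inclusion criteria ask for "peripheral IV catheter access placed that is anticipated to last a minimum of 24 hours", which is an expectation; the hard floor is a modelling choice.

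Formulas, t in days:
- 1 − KM(t) = 1 − exp(−ht)
- CIF(t) = 1 − exp(−h) + exp(−h) × h/(h+g) × [1 − exp(−(t−1)(h+g))]

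Central case, day 7: 1 − exp(−0.70) = 0.503. CIF = 0.0952 + 0.9048 × 0.2857 × (1 − 0.1225) = 0.322.

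Central case, day 3: 1 − exp(−0.30) = 0.259. CIF = 0.0952 + 0.9048 × 0.2857 × (1 − 0.4966) = 0.225.

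| | Day 3 | Day 7 |
|---|---|---|
| 1 − KM, central case | 25.9% | 50.3% |
| Cumulative incidence, central case | 22.5% | 32.2% |
| Ratio over the whole range of h and g | 1.06–1.31 | 1.14–2.24 |

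Without the 24-hour floor, CIF(7) = h/(h+g) × [1 − exp(−7(h+g))] = 26.1%, so the gap widens.

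**A between-group reduction, if one is taken from the curves.** Halve h from 0.10 to 0.05 in one group, with g = 0.25 in both.
- Day 3: 1 − KM is 25.9% and 13.9%, a reduction of 12.0 points (46.3% relative). CIF is 22.5% and 12.0%, a reduction of 10.5 points (46.6%).
- Day 7: 1 − KM is 50.3% and 29.5%, a reduction of 20.8 points (41%). CIF is 32.2% and 18.1%, a reduction of 14.1 points (44%).

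The absolute distortion does not always go the same way. With a control rate of 0.50/day, the day-7 reduction is 14.4 points by Kaplan-Meier against 20.2 by cumulative incidence.

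**The separate inconsistency.** This needs no arithmetic. One sentence rules out a hypothesis test for the secondary objective, and part (a) then names Chi-square and Fisher's exact test, which are hypothesis tests. Poisson regression can serve estimation alone.

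**The case against.** **The right proportion may be reported anyway.** Chi-square and Fisher's test work on crude counts. Add a drop-out rate of 0.026/day to the central case, which gives about 10% drop-out, and keep those patients. The crude day-7 proportion is (0.10/0.126)(1 − exp(−0.126)) + exp(−0.126)(0.10/0.376)(1 − exp(−6 × 0.376)) = 0.094 + 0.210 = 30.4%, against 32.2% for cumulative incidence. This stands: the crude figure is close. But the SAP assigns the proportion to Kaplan-Meier, so the mislabelled figure would appear beside it.

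**The day-7 figures rest on a day the SAP does not name.** This also stands. In the central case about 66 × 0.9048 × 0.1225 = 7 of 66 patients per arm are still at risk at day 7. At day 3 the gap of about 3 points is smaller than one standard error of a proportion, √(0.23 × 0.77/66) ≈ 5 points. That is why both days are shown.

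**The censoring clause sits in part (b) and is permissive.** True, but Kaplan-Meier is the only named method to which a censoring time naturally applies, and no other handling is given for part (a). Both documents are synopses, so a fuller plan may name the readout day and define the Per Protocol population.

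**Stronger readings that the documents do not support.** A reader might infer that the estimated benefit of the device is inflated. The SAP specifies no Kaplan-Meier difference: its between-group sentence names Chi-square, Fisher or Poisson methods. Even where a difference is taken from the curves, the direction of the absolute distortion depends on rates that the documents do not give. A reader might also infer that the figure is simply the 7-day risk with the IV left in. That holds only if therapy end is independent of complication risk.

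**Conclusion.** The point holds for one secondary estimate. Read naturally, the plan yields a percentage that is never below the proportion it names and generally above it. That direction is certain; the size is not, since it rests on assumed constant, independent rates and an assumed readout day. Over the ranges tried the overstatement is modest at day 3 and can exceed twofold at day 7. Any effect on a between-group reduction read from the curves is small at day 3 and larger at day 7 in the central case. The primary non-inferiority and superiority tests, the sample size and the named crude or Poisson comparisons are untouched. The SAP should be corrected, but the trial's main conclusion is not at risk.

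The conflict over hypothesis tests is a genuine but minor wording inconsistency. It is independent of the censoring point and adds no weight to it.

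**What to change.** Estimate the proportion by cumulative incidence (Aalen-Johansen), with normal end of therapy without a prior complication (discharge or IV discontinuation) as the competing event. Censor only at day 7 and at drop-out while still on therapy, and state whether such drop-outs remain in the Per Protocol population. Name the readout day and report the between-group difference on that day with a 95% CI.

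If Kaplan-Meier is kept, label it as the risk by the named day had the IV stayed in place, assuming that therapy end is independent of complication risk. Do not present it as the proportion during therapy.

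Separately, reconcile the statement on hypothesis tests with the methods named. Report differences in proportions and a Poisson rate ratio (log follow-up time as offset) with 95% CIs. Drop the Chi-square and Fisher p-values or label them exploratory.

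**Cost:** SAP wording and standard software. The reason for exit, normal end or drop-out, must be recorded for each patient, and the reported percentages will be smaller than the Kaplan-Meier ones. Relabelling alone costs only wording. Neither route changes the primary test or the sample size.

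### The secondary objective is declared estimation-only but is given chi-square and Fisher tests; no between-arm effect measure or interval is named, and the count model's exposure and variance are left open

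*SAP*

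**What the plan says.** The aim, in the SAP row SECONDARY OBJECTIVES, is estimation: "The secondary objective is to estimate the reduction of other peripheral IV (PIV) catheter mechanical complications". The STATISTICAL ANALYSIS row repeats this: "The secondary objective does not include a hypothesis test; estimation techniques will be used".

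Under To analyze Secondary Objective, item a has two parts.

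- For estimation, the proportion of patients with a complication "will be estimated using a Kaplan-Meier time-to-event analysis".
- For the comparison of arms, the text reads: "The proportions and counts of total mechanical complications will be compared between groups using a Chi-square analysis". Two alternatives to chi-square are then offered, namely Fisher's exact test "or Poisson regression as appropriate".

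Item b lists the endpoints as rates: "Secondary endpoints include rates of IV restarts, blood/fluid spillage, dislodgement, infiltration, phlebitis, occlusion, and infection". It adds that "the analysis method permits censoring at the time the patient exits or completes the study if this is prior to 7 days".

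The Protocol row on duration of participation says that subjects are "followed for up to 7 days, or until the patient is discharged, or until IV access is discontinued", so time at risk differs between patients.

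Neither document names a rate ratio, risk difference or confidence interval for the between-arm comparison. Neither states an exposure term or a variance method for the counts.

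**The concern.** There are two problems, and the first needs no calculation.

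1. **Conflicting statements.** A reader cannot tell whether secondary p-values will be reported. Chi-square and Fisher's exact test return p-values; neither estimates a reduction. Poisson regression can estimate a ratio, so the conflict is with the two tests only.

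2. **Counts of total complications.** If the aim is estimation, the interval is the result. A chi-square on total counts, or Poisson regression with its model variance, treats every complication as an independent event. Recurrence within a patient is an inference, drawn from the reference to counts of total complications and from restarts being an endpoint. If some patients are more prone to complications than others, the interval is too narrow. If follow-up also varies and the model has no exposure term, that variation adds further unmodelled spread.

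**Working it through.** **Plan figures.** The only sample-size figures are 66 per group and 10% added: 66 × 1.10 = 72.6, so 73 per arm and 146 in total, as stated. These belong to the primary test. I use 66 per arm as the arm size. The documents give no complication rate, dispersion or mean follow-up, so **every other input below is assumed**.

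**Formula at equal follow-up.** Let a patient's count have mean m, and let the relative rate vary between patients with variance v (gamma-Poisson). The count variance is m(1 + mv), where Poisson assumes m. A nominal 5% comparison of two equal arms then has error

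2 × [1 − Φ(1.96 / √(1 + mv))].

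- m = 0.4, v = 0.5: 1 + mv = 1.2; 1.96/√1.2 = 1.79; error 0.074 (simulated 0.072).
- m = 1.0, v = 2: 1 + mv = 3; 1.96/√3 = 1.13; error 0.258 (simulated 0.257).
- v = 0: error 0.05.

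The correct standard error exceeds the Poisson one by √(1 + mv), which is 1.10 and 1.73 in the first two cases.

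**Simulation, equal true rates.** 66 per arm, m from 0.4 to 1.0 (66 × 0.4 = 26 to 66 × 1.0 = 66 expected events per arm), 20,000 trials per cell. Plain Poisson uses the log count ratio over √(1/a + 1/b), where a and b are the arm totals.

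| Analysis | Follow-up | v = 0 | v = 0.5–2 |
|---|---|---|---|
| Plain Poisson, no offset | equal | 5% | 7–26% |
| Plain Poisson, no offset | uniform on 1–7 days | 6–7% | 8–29% |

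Offset plus robust variance gives 5.0–6.4% over the grid, and up to about 7% under another assumed follow-up pattern. An offset alone is not enough: with v = 0.5–2 the error is still 7–28%. At a true rate ratio of 0.6, the 95% interval without offset misses the truth 6–25% of the time; with offset and robust variance, 4.9–6.7%.

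**Rare single endpoints.** At m = 0.05–0.1 (66 × 0.05 = 3.3 to 66 × 0.1 = 6.6 events per arm), follow-up uniform on 1–7 days and v = 0–2, plain Poisson without offset errs about 1–5%, leaving out trials with an empty arm. The formula above is a large-count approximation and does not apply there.

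**Complications that end IV access.** Planned follow-up uniform on 1–7 days, each complication ending access with probability 0.3–0.9, daily rates 0.1–0.25.

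- Equal rates: follow-up is the same in both arms. Plain Poisson without offset errs 0.4–4.4% (v = 0) or 1.1–9.3% (v = 1); robust with offset 4.4–5.8%.
- True daily rate ratio 0.6: the arm with fewer complications is followed longer (for example 2.98 v 2.50 days at rate 0.25, probability 0.9, v = 0). The estimated ratio is 0.61–0.71 without offset and 0.59–0.60 with it (v = 0), or 0.62–0.74 and 0.61–0.65 (v = 1). At v = 1 the offset reduces the bias but does not remove it.

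**Sparse endpoints.** With 0 events in 66 patients, the Kaplan-Meier (Greenwood) variance is zero, while the exact 95% upper limit is 1 − 0.025^(1/66) = 5.4%. With 1 v 3 events at equal exposure, the exact rate-ratio interval is 0.006–4.15.

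**The case against.** The SAP is a registry synopsis, and an offset or variance estimator is detail that such a text often omits. Item b speaks of rates, Poisson regression of rates is usually fitted with exposure, and the wording leaves room for both features. The censoring sentence follows the list of rates, so the SAP does acknowledge unequal follow-up. All of this stands: the count model is unspecified, not shown to be wrong. The open choice of method still commits to nothing before the data are seen.

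The conflict over testing also has a mild reading: no formal hypothesis is set, and the named methods accompany a descriptive comparison. No secondary alpha or success claim appears. That reading is reasonable, but the SAP has to say so, and it still lacks an effect measure and interval.

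The size of the problem is assumed and has no settled direction. This stands too: no passage supports a between-patient variance of 0.5–2, and where complications end access plain Poisson may be conservative. Finally, the crude proportion of patients with a complication over their own course of therapy is a legitimate quantity; preferring a Kaplan-Meier difference is a choice of estimand, though it matches the estimate that item a already plans.

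**Conclusion.** The point holds as a minor one. The conflict between an estimation-only objective and named tests is in the text and rests on no assumption. The statistical consequence is conditional: error of about 7–29% at nominal 5% for total complications if patients' rates vary as assumed, against 5–6% with offset and robust variance; little or no inflation without heterogeneity or for rare endpoints.

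The documents do not support four stronger readings that a reader might infer.

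- *The count analysis will be anti-conservative.* They give no rate or dispersion, and the direction can reverse.
- *Follow-up will differ by arm and produce false positives.* Nothing shows such a difference, and at equal rates complication-led discontinuation does not create one.
- *The Kaplan-Meier result is unreliable at day 7.* The SAP specifies no day-7 readout, and the number at risk then depends on a follow-up distribution that is not given.
- *Seven endpoints tested at 0.05 give a 30% chance of a false positive* (1 − 0.95^7 = 0.30, assuming independence). The SAP sets no secondary significance level and makes no such claim.

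The primary test and the sample size are unaffected.

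**What to change.** Amend the STATISTICAL ANALYSIS row of the SAP as follows.

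- State that secondary comparisons are descriptive, with no significance claims, and remove the chi-square and Fisher tests or reconcile them with that statement.
- For total complications and other counts that are not sparse: the rate ratio with 95% CI from Poisson regression, with log(days at risk) as offset and robust patient-level variance.
- For any-event proportions: the between-arm Kaplan-Meier difference with 95% CI. The sponsor should name the time at which it is read.
- For sparse endpoints: counts per arm with exact intervals.

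The cost is wording only. Days at risk are already needed for the censoring and for the per-24-hour primary measure. The downsides are that there will be no secondary p-values, and that count intervals will be wider on the log scale if there is overdispersion: by the formula above, 10–73% over the assumed range, and essentially unchanged if there is none.
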